We hypothesize this rehabilitation strategy will also be successful in human subjects. The proposed project aims to translate animal hemianopia research to a noninvasive rehabilitation system for use by human visual hemianopia patients. The specific objectives of the program can be enumerated as follows:

Specific Aim 1: Determine the efficacy of an intervention using cross-modal stimulation training to restore visual function in homonymous hemianopia patients.

Specific Aim 2: Assess the long-term effects of rehabilitation through follow-up visits after the completion of rehabilitation.

Methods and Measures

Design

This study will test a rehabilitation technique for treating visual hemianopia and compare results against measures from patients pre-intervention. We will recruit all interested patients with visual hemianopia and will assess visual field, visual capabilities, quality of life, and brain images as part of our research measures.

Setting

Rehabilitation training sessions and progress tests will be performed on the Wake Forest Baptist Medical Center Campus and in subjects' homes. Since administering the Humphrey visual field test requires specific equipment, subjects will visit an optometrist's office for these tests. Subjects will perform the remaining visual tests on the Wake Forest Baptist Medical Center Campus.

Subjects selection criteria

- **Inclusion Criteria**
 - Adult volunteers diagnosed with homonymous visual hemianopia / hemianopsia (ages 18-99)
 - MRI or CT scan demonstrating lesion in the occipital lobe of the brain and/or affecting white matter tracts that provide visual input to the occipital lobe of the brain
 - Brain injury due to ischemic or hemorrhagic causes that occurs after age 18 and at least 6 months prior to screening visit
 - Demonstration of good fixation on visual training task
- **Exclusion Criteria**
 - Volunteers who are unable to complete the study tasks or understand instructions
 - Subjects that are not able to provide written consent or verbal assent
 - Subjects who are not available to complete all rehabilitation sessions
 - Physical, neurological or mental disability that would interfere with study intervention
 - Concurrent participation in "vision therapy" other than standard occupational or physical therapy

- **Sample Size**

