Testing: Possessing the ability to localize sound is essential in properly implementing the rehabilitation strategy, which relies on subjects to respond to auditory and visual training stimuli. As part of the screening process, subjects' ability to detect the approximate location of sound will be assessed. Subjects will be asked to fixate on a light straight ahead and be presented with sound from 15° or 45° on either the left or right side. The location of the sound will be randomly picked by a computer program. Subjects will be asked to identify the side the sound originated from and the approximate location. Study staff will log these responses on a computer. Subjects with responses accurate 90% or higher will be considered to have passed the test and be eligible for the study.

This test will be conducted using the free-field frame device (fig 1), which uses a semicircular frame to hold LED lights and 4 speakers fixed to 15° and 45° positions. Eye tracking or a camera recording of the subject's eyes may be used to ensure the subject is properly fixating on the light. The eye tracking camera may take photographs and video for the study team to later review. If a subject cannot maintain visual fixation or identify the origin of sound, the visit and study will end and they will be compensated \$40 for their travel.

[figure not shown]

Figure 2: Study Timeline

To verify their hemianopia condition, subjects will be asked to provide relevant medical records, which will be used to confirm diagnosis. Subjects will be instructed to bring their medical records, with proof of hemianopia diagnosis, to the screening visit. After they have passed the sound localization and visual fixation test, a study member will review these records to make sure the subject is eligible to continue the study. Since the effects of hemianopia can vary between patients due to the extent and location of brain damage, copies of relevant records may be kept to aid data analysis. These copies will be kept in a locked and secure storage location. Patients will be assigned a subject id and any identifying personal information will be redacted from these copies. If the patient is deemed ineligible during the study, any copies made of these records will be promptly destroyed.

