During this visit, baseline measurements for subjects will be obtained. Subjects will undergo a peripheral visual field test and be asked to complete 2 quality of life questionnaires: the National Eye Institute Visual Function Questionnaire (NEI VFQ-25) and the Veterans Affairs Low Vision Visual Function Questionnaire (VA LV VFQ-48). Subjects are expected to spend up to 2 hours for this visit.

(Optional) Study Session 2: Pre-Intervention Test - Humphrey Visual Field Test (1 hour)

Subjects will report to an optometrist, who will administer the Humphrey Visual Field Test, using a size V stimulus. This visit will be separate from the other pre-intervention tests due to the special equipment needed for the Humphrey Visual Field Perimetry. This visit is expected to take up to 1 hour. This visit may be omitted if subjects have a recent Humphrey Visual Field Perimetry test result and gives the study team permission to view and keep a copy of the result.

Study Sessions 3 – 32: Cross-Modal Rehabilitation Training (30 minutes each day)

Each cross-modal rehabilitation training session will take place either on the Wake Forest Baptist Medical Center Campus or in subjects' homes, if subjects find traveling to the Wake Forest campus to be too difficult to do daily. For patients who are performing rehabilitation at home, the study team will regularly call and check-in with the subject in order to make sure the patient is not experiencing any problems. The VR rehabilitation system will send data such as duration of rehabilitation and progress test results through a cellular network, in order to monitor compliance and track rehabilitation progress. The data will only be linked to a study identifier to maintain privacy. Initial rehabilitation sessions will be done at the Wake Forest Baptist Medical Center campus to ensure subjects understand how to use the rehabilitation device and are capable of performing rehabilitation at home.

In each rehabilitation session, subjects will sit down, put on a virtual reality headset with a pair of headphones, and use a button on a handheld controller to interact with the rehabilitation system. In order to make sure subjects are correctly performing rehabilitation, the headset may be outfitted an eye tracking system consisting of a camera and low intensity infrared lights to collect data on patient's eye movements.

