The virtual reality headset and headphones will provide visual and auditory stimulation used in the rehabilitation training. Each rehabilitation session will consist of 200 trials. At the end of each rehabilitation session, subjects will perform a brief 2-minute VR visual field progress test with the VR system to track rehabilitation progress. The rehabilitation will be considered complete once patients can reliably detect stimuli 45° in the hemianopic field.

If patients cannot detect stimuli at 15° by the end of 30 days of rehabilitation, they will repeat the rehabilitation for one more month, in order to determine if the slow progress or lack of progress is caused by simply not spending enough time performing rehabilitation.

Study Session 63: Post Rehabilitation Tests - Subject visual field did not increase (1 hour)

If no visual field improvement (measured by virtual reality visual field progress tests) has occurred at the end of the 2nd round of rehabilitation, subjects will complete one last visit, where they will be given the

NEI VFQ-25 and VA LV VFQ-48 questionnaires to complete. This visit will occur on the Wake Forest Baptist Medical Center campus.

Study Session 33: Post Rehabilitation Tests - Subject visual field increase (1.5 hours)

If a subject shows visual field expansion in the virtual reality visual field progress test, subjects will be given a **Peripheral Visual Field Test, NEI VFQ-25 and VA LV VFQ-48 Questionnaires** in order to measure visual field expansion and improvements in quality of life.

In previous animal studies, rehabilitated hemianopic animals could only detect spatial frequencies of 2 cycles/degree compared to over 5 cycles/degree in the (normal) intact animals. We hypothesize the subcortical visual pathway mediating the restored visual functions may not have the same capabilities as the visual cortex it is replacing. Therefore, recovered vision may have lower visual acuity. The different pathways involved in cross-modal rehabilitation may also affect abilities for shape recognition in the newly recovered visual field. We will explore whether this is the case with a simple **shape recognition test, visual acuity test, and color vision test** during this visit. Subjects will complete this visit on the Wake Forest Baptist Medical Center campus.

Study Session 34: Humphrey Visual Field Post-Intervention Test (1 hour)

Subjects will report to an optometrist for a **Humphrey Visual Field** perimetry test.

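### Entry sets no minimum measured field loss, so a subject who already detects at 45° can enrol, meet the completion rule unchanged and fit neither post-training route

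*Combined protocol and SAP*

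**What the plan says.** Under Subjects selection criteria, the field defect enters as a diagnosis: "Adult volunteers diagnosed with homonymous visual hemianopia / hemianopsia". A second criterion concerns imaging: "MRI or CT scan demonstrating lesion in the occipital lobe of the brain and/or affecting white matter tracts". The injury must be at least 6 months old and fixation must be good. Neither the inclusion nor the exclusion list states an extent or depth of field loss.

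Under Study Session 1 the protocol says: "To verify their hemianopia condition, subjects will be asked to provide relevant medical records, which will be used to confirm diagnosis". It continues: "a study member will review these records to make sure the subject is eligible to continue the study". No limit is put on the age of the records. The only numeric threshold at screening concerns hearing: "Subjects with responses accurate 90% or higher will be considered to have passed the test and be eligible for the study". The field test appears as baseline data: "Subjects will undergo a peripheral visual field test and be asked to complete 2 quality of life questionnaires". Humphrey perimetry at Session 2 is optional, can be replaced by a recent result (recent is not defined), and has no threshold either.

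Under Study Sessions 3–32: "The rehabilitation will be considered complete once patients can reliably detect stimuli 45° in the hemianopic field". Two routes follow. Subjects who cannot detect 15° after 30 days repeat the month. Subjects whose VR progress test shows expansion go to Session 33, which includes the frame test. Session 63, for subjects with no improvement after the second round, lists questionnaires only.

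Outcome Measure(s) names the Humphrey and frame tests, before versus after, as primary for all participants, and the VR progress test as secondary. Sample Size assumes 80% success with 5 subjects and does not define success.

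**The concern.** Specific Aim 1 is about restoring visual function. A subject with no measured loss at 45°, the location on which the Objectives section says the strategy is focused, cannot show restoration there. The written criteria would admit that subject, because a past diagnosis and a lesion on a scan do not establish what the subject detects on the day of screening. The protocol itself notes under Study Session 1 that the effects of hemianopia vary with the extent and location of the damage.

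Completion is an absolute state, not a change, so such a subject could be recorded as having completed rehabilitation with nothing altered. The Sample Size section intends the observed response pattern to inform incidence estimates for later studies. With about 5 completers, one subject carries a fifth of the weight.

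**Working it through.** **Inputs.** Frame test: 15°, 30°, 45°, 60° and 75°, 5 trials each, so 5 × 5 = 25 hemianopic-side trials (Peripheral Visual Field Test). VR progress test: 15°, 30° and 45° (test descriptions under Tests). Success 80%, n = 5, half-width 0.35 (Sample Size).

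**The plan's own figure.** Half-width = 1.96 × √(0.8 × 0.2 / 5) = 0.3506. The stated 0.35 is reproduced, and this point does not dispute it.

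**Room to improve.** Assume the subject detects every trial out to a limit and none beyond, and that the VR and frame tests agree at a given azimuth. Room = locations not yet detected ÷ locations tested.

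| Baseline limit | Frame score | Frame room (points) | VR room (points) |
|---|---|---|---|
| none seen | 0% | 100 | 100 |
| 15° | 20% | 80 | 67 |
| 30° | 40% | 60 | 33 |
| 45° | 60% | 40 | 0 |
| 60° | 80% | 20 | 0 |
| 75° | 100% | 0 | 0 |

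A subject who detects out to 45° scores 15/25 = 60% on the frame test and keeps 10 trials (40 points) at 60° and 75°. On the VR test there is no room. Room on the Humphrey test cannot be computed from the documents.

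**Effect on the mean.** If the other 4 completers start at 0%, the maximum mean gain is (4 × 100 + 40) / 5 = 88 points, against 100: a loss of 12. With two such subjects it is (3 × 100 + 2 × 40) / 5 = 76. If all 10 recruits complete and one is of this kind, it is (9 × 100 + 40) / 10 = 94, a loss of 6.

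**Effect on the success proportion.** Success is undefined, so both readings below are assumptions, with 80% success among the others and n = 5.

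| Such subjects | Success = detects 45° | Same, no treatment effect | Success = a gain, none shown by these subjects |
|---|---|---|---|
| 0 | 0.80 | 0 | 0.80 |
| 1 | (1 + 0.8 × 4)/5 = 0.84 | 1/5 = 0.20 | 0.8 × 4/5 = 0.64 |
| 2 | (2 + 0.8 × 3)/5 = 0.88 | 2/5 = 0.40 | 0.8 × 3/5 = 0.48 |

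**Routes after training.** The subject detects 15°, so the repeat month does not apply. Already at the VR ceiling, the subject cannot show VR expansion, so the condition for Session 33 is not met. Session 63 follows only a second round. As written, no session description triggers the immediate post-treatment frame test, although Outcome Measure(s) expects primary measurements from everyone. The VR test is given only at the end of training sessions, and the protocol says the Humphrey test reaches only 30°. The Session 1 frame test is therefore the only scheduled pre-training measurement at 45°.

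**The case against.** The case on the other side is substantial. The Design section says all interested patients with hemianopia will be recruited, so broad entry is a stated choice. The study is exploratory and will report the response pattern; with about 5 completers, each subject's baseline and final fields can be shown. The Background describes hemianopia as blindness in one hemifield. The primary outcomes are before/after comparisons, and the 45° rule says when training is complete; it is not an endpoint.

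Much of this stands, and it rules out several stronger readings that a reader might infer:

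- That hemianopia is accepted on records alone. Records are the only stated check on the field defect, but a lesion on imaging is also required.
- That such a subject has little room to improve on the primary measure. This is true of the VR test only; 40 points remain on the frame test.
- That such a subject would inflate the success rate. This follows only if success means detecting 45°. If success means a gain and the subject shows none, the rate falls instead.
- That such enrolment is likely. The documents give no rate.

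What the objection does not do is close the gap. A description in the Background is not an entry criterion, and a baseline value that no rule uses does not decide how the subject is classified. Nor does the change-based primary outcome help if the session descriptions do not trigger the post-treatment frame test.

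**Conclusion.** The gap is real, and its effect is moderate. No passage requires a measured field loss at entry, and the Session 1 frame test has no role beyond baseline. A subject already detecting at 45° satisfies the completion rule unchanged, has no room on the VR test and matches neither post-training route.

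The size, for one such subject among 5 completers, is 12 points off the maximum mean frame-test gain. If success means detecting 45°, it is also 20 points on the success proportion with no treatment effect. These figures assume complete detection out to 45° and none beyond, the other completers starting at zero on the frame test, and agreement between the two tests. Frequency is unknown, so this shows what the written rules permit and does not forecast bias.

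**What to change.** Before training starts, use the Session 1 frame test to identify subjects with no measured deficit at 45° on the hemianopic side. Prespecify one of two rules:

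- **Entry criterion.** Require a measured deficit at 45°, with a limit chosen by the sponsor that does not reject subjects who see only at 15°. A limit pooled over 15° to 45° would be a poor choice. A subject who sees only 15° scores 5 of 15 and could be rejected despite 80 points of room, while one who sees only 60° and 75° scores 0 of 15 and passes with a 10/25 = 40% baseline.
- **Separate reporting.** Enrol these subjects, keep them in the before/after comparison, report them separately and leave them out of the success proportion.

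Under either rule, define success as a change from the subject's own baseline, and give every subject the post-treatment frame test whatever the VR result. The completion rule and the two routes should also be reconciled for a subject who detects 45° from the start; how is for the sponsor to decide.

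No new test is needed. The entry criterion may cause a few screen failures against a target of 10. It also selects on the outcome's own baseline, with only 5 trials at 45°, which invites some regression to the mean in an uncontrolled comparison. Separate reporting loses no enrolled subject and limits that problem, because everyone stays in the before/after comparison. It shrinks the success denominator: with 4 of 5 counted at 80%, the half-width becomes 1.96 × √(0.8 × 0.2 / 4) = 0.39 instead of 0.35. Adding the post-treatment frame test costs some visit time for subjects who would otherwise not have had it.

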Auditory stimulus consists of a brief burst of white noise, lasting approximately 100 ms. Visual stimulus is a white colored orb positioned against the dark, neutral background and will be displayed for 1-2 seconds. The longer duration of the visual stimulus will serve to provide stimulus location feedback for patients. Patients will be instructed to orient their eyes and head toward stimuli in the hemianopic field and to push a button on a controller upon detecting stimuli. This part of the task will serve to boost motivation and maintain attention during training. The software will also record these responses and reaction times, based on the button presses, and store this data for later review. The next trial will begin 3-4 seconds after the visual or auditory-visual stimulus disappears and when the patient re-fixates on the fixation point.

Cross-modal visual auditory rehabilitation consists of a total of 200 trials / day (about 30 min) over 1 month. Given the results from animal model studies, we expect progress to be observable after 2-3 weeks of cross-modal rehabilitation, and completion of rehabilitation 1 month after the start of cross-modal training.

While we expect most patients will perform rehabilitation using the virtual reality rehabilitation system, patients may also complete rehabilitation with a free-field frame device if they are not comfortable with using a VR headset. The free-field frame device uses a semi-circular frame to hold LED lights (visual stimulus) and speakers (auditory stimulus) in front of the patient. These lights and speakers can be used to deliver the same cross-modal visual auditory rehabilitation paradigm. The device is also used to perform peripheral visual field tests, and is described in more detail below in *peripheral visual field test*.

Tests

Humphrey Visual Field (HVF) Test - The HVF test is a common test given to map the visual field. During the HVF test, light is projected into a white bowl with a standardized background light intensity to form a circular stimulus, around 30 cm away from the patient's eye. The overall field mapping technique used is a form of static perimetry, where a stimulus appears in various areas of the field of vision. The patient indicates when they can see the stimulus and the perimetrist then records the point where the stimulus was seen. These datapoints are used to determine the patient's visual field.

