Peripheral Visual Field Test - Since the Humphrey visual field test only measures up to 30° in the periphery, an additional peripheral visual field test will be administered using a semi-circular frame device (fig. 1) set 50 cm in front of the subject with LED lights acting as visual stimulus, located at azimuths of 15°, 30°, 45°, 60°, and 75°, as well as a center fixation light. Lights will be presented at a random time with a fixation period between each trial and locations selected randomly. Subjects will be asked to fixate on the center fixation light while lights are presented at random locations at random times (0-1.5 seconds). Upon detecting a light, subjects will press a button. Subject responses will be used to determine how far in the periphery, up to 75°, a subject can see. The test will present a total of 5 trials at each location in both the intact and hemianopic side, as well as 5 trials with no stimuli.

This test uses the free-field frame device to position visual and auditory stimuli, in the form of LED lights and speakers, at different angles of the patient. The patient is asked to maintain visual fixation on a lit LED light straight ahead during the test. Speakers will play a brief burst of white noise from a random location 15° or 45° on either the left or right side. The subject will be asked to identify where the sound is originating from either verbally or using a button response pad. During this test, subjects' eyes may be videotaped or photographed. These recordings or photos will be reviewed by a member of the study team to confirm the subject is able to properly maintain visual fixation.

Figure 1: Free-field frame device

track rehabilitation progress. The test consists of 30 trials with visual stimulus presented either 15°, 30°, 45° in either the hemianopia field or the intact field at random time intervals.

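### The Humphrey field before and after training need not use the same settings, and an outside baseline may replace Session 2 with no technical condition or maximum age

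*Combined protocol and SAP*

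**What the plan says.** Under Outcome Measure(s), the Humphrey field and the peripheral frame test are the primary outcomes for every participant, compared before and after treatment. The Design section makes the subject's own pre-intervention measurement the only comparator.

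The pre-training Humphrey test is Session 2, labelled optional. The subject goes to an optometrist, "who will administer the Humphrey Visual Field Test, using a size V stimulus". The same paragraph then allows a substitute: "This visit may be omitted if subjects have a recent Humphrey Visual Field Perimetry test result". The only other condition is that the subject "gives the study team permission to view and keep a copy of the result". *Recent* is not defined.

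The post-training test is Session 34. Its text says only that subjects go to an optometrist for Humphrey perimetry. It does not refer back to Session 2.

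The general description under Tests calls the technique "a form of static perimetry, where a stimulus appears in various areas of the field of vision", with a standardized background, a circular stimulus and a distance of about 30 cm. The Peripheral Visual Field Test section adds that "the Humphrey visual field test only measures up to 30° in the periphery". Neither section gives a stimulus size, a named pattern or a strategy.

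For subjects with no improvement on the virtual reality progress test after a second month of training, the Session 63 text says "subjects will complete one last visit" and lists only the two questionnaires.

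**The concern.** A within-subject comparison without a control group depends on measuring the same thing in the same way twice. By the plan's own description, the field is built from the points at which the subject reports seeing the stimulus. It therefore depends on what is shown and where. If those settings change between the two tests, part of the difference may come from the test. If the baseline is an outside result of unknown age, part may come from change before training began.

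The design has no second group in which either component could be estimated. An in-study baseline that was waived cannot be taken once training has started. The study is meant to inform future trials, so an artifact in a primary outcome could carry forward into their planning.

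**Working it through.** The plan gives no figure on this point. Its one computed figure, in Sample Size, reproduces: 1.96 × √(0.8 × 0.2 / 5) = 0.351, against 0.35 stated. That figure concerns the success proportion and has no bearing on test settings. Only its inputs (80%, n = 5) are used below.

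**Step 1. Compare the described sources of Humphrey data.**

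| Item | Session 2 | Outside result | Session 34 |
|---|---|---|---|
| Stimulus size | V | not set | not set |
| Test pattern | not set | not set | not set |
| Strategy | not set | not set | not set |
| Timing | before training | *recent*, undefined | after training |

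Size is fixed for 1 of 3 sources, and pattern and strategy for 0 of 3. The features common to all three are the generic ones in the Tests section.

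**Step 2. Follow the two routes to a baseline.**
- In-study baseline: size V before training and no stated size after it. Pattern and strategy are open at both visits. A match is likely if the same office repeats its own test, but the text does not require the same office or the same test.
- Outside baseline: no setting is required at either test, and the age of the first is unlimited apart from the word *recent*. The team holds a copy, so a mismatch could be noticed. No rule says to look for one or what to do about it.

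**Step 3. What is affected.** The peripheral frame test has its baseline at Session 1 with no waiver, and its distance, azimuths and trials per location are specified. The two-way ANOVA in the Analytical Plan uses that test. The gap is therefore confined to the Humphrey outcome.

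**Step 4. Weight of one subject.** With the five completers the plan hopes for, one mismatched pair is 1/5 = 20% of the Humphrey comparison. How many pairs would be mismatched is not derivable.

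**Step 5. Who has a post-training test.** Outcome Measure(s) gives visits 34 and 35, or 63 and 64, as the after-treatment visits for everyone. Session 63, as described, is a questionnaire-only final visit for subjects without improvement, and visit 64 is not described. Visits 63 and 64 may be meant for subjects who improve during a second month, but the text does not say so. At the assumed 80% success, and taking success to mean improvement on the progress test (an assumption), (1 − 0.80) × 5 = 1 of five completers would have no described post-training Humphrey field.

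**The case against.** Four arguments on the other side have some force.

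- The plan is not silent. The general description covers every session, and the waiver does require a recent result and permission to keep it. A reader might infer that nothing at all supports comparability. That goes too far: what is missing is any technical condition and any age limit.
- Settings could be matched the other way round. Session 34 fixes nothing and the team keeps the outside result, so the post-test could be run at that subject's baseline settings. This would restore the within-subject comparison as far as settings go. The plan does not ask for it, however. It would also leave subjects measured by different tests, and it does nothing about an old baseline.
- The study is exploratory, and no Humphrey summary measure or Humphrey-specific test is named. This limits the priority. It does not remove the point, because Humphrey is still declared primary.
- A reader might infer that an outside test done less than six months after the injury breaches the plan's own criterion. The documents do not support this. That criterion concerns eligibility at screening, and nothing says it exists because fields change before then. A maximum age for the outside result is the better-grounded control.

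The timeline figure was not readable in the text reviewed. If it states test settings, the point narrows accordingly.

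**Conclusion.** The point holds in limited form. The protocol can be followed exactly and still pair a baseline with a post-test run at different settings, or with a baseline of unstated age, for a primary outcome that has no other comparator. In such a subject the change cannot be attributed to training.

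A reader might infer that the Humphrey results will be biased, or biased towards benefit. The documents do not support either: they do not show how often the waiver would be used, which settings outside tests would have, or which way a mismatch would push the result. Nor do they support a claim that the frame-test ANOVA is compromised.

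This should be corrected before further subjects are enrolled. The 20% weight per mismatched subject assumes five completers. The count of one subject without a described post-training test assumes the 80% rate and equates success with improvement on the progress test.

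**What to change.** 1. Name one pattern and one strategy, with size V as already set for Session 2. Require Session 34, and any other post-intervention Humphrey test, to use the same size, pattern and strategy as that subject's baseline.
2. Accept an outside result as baseline only if it used size V and the study's pattern and strategy, and falls within a maximum age before the first training session. The sponsor should choose and state that maximum.
3. Otherwise hold Session 2.
4. Separately, reconcile Outcome Measure(s) with the Session 63 text on whether subjects without improvement have a post-intervention Humphrey test, and describe visit 64. If they do have one, item 1 applies to it.

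Cost: protocol wording, plus at most 10 × 1 hour = 10 hours of Session 2 visits that the plan already contains. If item 4 adds a test for subjects without improvement, expect about one extra one-hour visit among five completers.
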